Aim I. Early Intervention: To determine the effects of early versus late rehabilitation for balance deficits in mTBI. We hypothesize that early rehabilitation initiated at the initial physician visit will improve outcomes more than standard of care (later initiation of physical therapy) in people with mTBI who have complaints of imbalance. We will also determine clinically meaningful change measures due to rehabilitation for objective measures of head stability during gait, based on Patient Global Impression of Change Scale (Hurst and Bolton 2004). We will randomize 160 people with mTBI, between the ages of 18 and 60, into early rehabilitation (within first 2 weeks after physician visit) or late rehabilitation (standard of care; ~60 days from first physician visit). People will be tested before and after a 6-week rehabilitation program and again 6 months later to determine long-term effects. Our primary outcome to measure efficacy of rehabilitation is the Dizziness Handicap Inventory (DHI). Secondary outcomes will be structured along the International Classification of Function and Disability (ICF) models framework. We will measure baseline peripheral vestibular and ocular motor function and other covariates in rehabilitation efficacy. In Aim I, we will 1) determine the role of timing in rehabilitation after mTBI and 2) determine meaningful change measures of novel head stability and gait metrics after rehabilitation.

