Subjects with an LAR must meet all inclusion criteria to participate in the research study. If all inclusion criteria are met the Legal Representative must complete an IRB approved 'Application & Certification for Waiver or Alteration of the HIPPA Authorization requirement' prior to participation in the study. This study will follow all rules and regulations of Title 10 United States Code Section 980 (10 USC 980).

6. Procedures InvolvedAim I & II

We will ask subjects their preferred contact method for appointment reminders (email, text message, or phone call). We will send participants IRB approved text/email templates for each appointment dependent on where their testing location is (VA or OHSU).

All testing visits will take approximately 3-4 hours and will take place at either OHSU or at the Portland VA (NCRAR). During the first two initial testing sessions over two days, participants will complete questionnaires to help identify how they perceive their problems, as well as undergo clinical tests of vestibular function and balance and gait. We will place five small (Apple Watch size) motion sensors on their waist, feet, trunk and head to measure balance and gait, and then will use a Neurocom platform to measure balance during a variety of sensory conditions. The platform moves and the participant stands as still as they can. They will be secured in a harness to eliminate the chance of falling. We will then have you perform several balance and gait assessments such as standing on one leg, tandem stance and feet together as well as walking tests such as continuously walking for approximately two minutes. If rehabilitation does not begin immediately, there will have one additional balance and gait testing session just prior to beginning rehabilitation. The two follow up testing sessions after the conclusion of rehabilitation will include the balance and gait testing but not the vestibular testing. The first follow up session will occur immediately after the 6 weeks of rehabilitation and the second follow up session will be an additional 6 months later.

Vestibular and cognitive testing session:

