The following tests and procedures will be performed a maximum of 4 times, depending on which physical therapy group participants were randomized into. Throughout this session, participants will wear 5 inertial sensors: 2 at the feet, 1 on the waist, 1 on the trunk, and 1 on the head to record the movements of each body segment. The sensors record accelerations, angular velocities, and orientation data and wirelessly transmit these data to a computer located across the room. No PHI / PII or identifiable data is included in this transmission.

Clinical and dynamic measures of balance, mobility and coordination: Participants will perform the Balance Error Scoring System consisting of 30 seconds of standing quietly in various conditions. They will also perform the mini-BEST, a standard clinical test of mobility that measures different elements of balance such as walking and going from sit to stand. They will also complete a complex turning task that involves motions similar to everyday movements around a home, where they will perform several walking turns in order to navigate a marked path multiple times. The time taken to complete the course will be recorded, and inertial sensors will record body movement. Eye tracking glasses will be worn and record the motion of the eyes during turning. Additionally, a 2-minute walk test will be performed at 1) a comfortable pace, 2) a comfortable pace while performing a secondary cognitive task. Clinical and instrumented assessment will occur simultaneously using a stopwatch and the inertial sensors. Participants will also wear eye tracking glasses to monitor the stability of their vision with respect to body movements. These tests will take approximately one and a half hours.

Oculomotor function and coordination: The coordination between participant's eyes and head will be assessed using a clinical assessment of vestibular and oculomotor function (Vestibular/Ocular-Motor Screening for Concussion – VOMS). Participants will wear the inertial sensors described above and the eye tracking glasses described above and then be asked to follow the researcher's finger in various configurations. Your vision will be screened using eye charts to test how clear letters are on a chart while seated and while moving your head. The researcher will ask then to report symptoms after each test. These tests will take approximately 15 minutes to complete.

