statistician using the Randomization Module to ensure half the participants receive the early intervention and half receive the standard of care timeline. Rehabilitation will last for 6 weeks with approximately one physical therapy session per week. During these sessions, the participant will be evaluated by the physical therapist and will perform exercises around commonly impaired areas such as balance performance, head movement, and aerobic exercise capability. They will be expected to do a home exercise program that is tailored to their ability level and you will either do this home portion as it is commonly prescribed or while using a wearable sensor to track head and trunk movements. They will be progressed in their rehabilitation program according to standard practice and by ability level. See appendix for specific details of intervention.

Functional Near Infrared Spectroscopy:

Functional Near Infrared Spectroscopy (fNIRS) is a noninvasive, mobile brain imaging modality that allows for reliable measures of cortical activity. Prefrontal cortex activity data will be collected on a subset of participants using a wireless portable, continuous-wave, functional 8-channel fNIRS system (OctaMon, Artinis Medical system) on the first and last rehabilitation session when performing aerobic exercise on the treadmill (Figure 9).

Adaptation during COVID- 19 restrictions: A study team member will send or deliver the wearable sensor technology to the subject's home. No physical contact will occur with patient. The physical therapist will do all rehabilitation intervention through a virtual visit. The home exercise program will be tailored to their ability and level.

Post testing: After the conclusion of physical therapy, subjects will be retested two times on the gait and balance testing but not the vestibular testing. The posttest session will occur after the 6 weeks of physical therapy. The follow-up session will be an additional 6 months later and will encompass the same testing protocol as the posttest session.

Home Monitoring:

Participants may be sent home with wearable sensors at pre-physical and post-physical therapy time points and wear the sensors for approx. 1 week. The wearable sensors will be worn for a minimum of 8 hours each day and collect the participant's activity and mobility metrics.

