To compare the effect of early versus late intervention, the main effect of time (Aim I, comparing groups AB to CD) will be assessed in the mixed-effects model. To compare the effect of rehabilitation with home monitoring versus standard-of-care rehabilitation, the main effect of treatment will be assessed in the mixed-effects model (Aim II, comparing groups AC to BD). To compare whether the effect of at-home monitoring is different between early and late rehabilitation, the interaction between time and treatment will be evaluated using the mixed-effects model. Beyond the main effects of time, treatment and their interaction, individual contrasts among groups will be considered using an ANOVA framework to compliment mixed-effects regression model.

Mixed-effects models will also incorporate covariates found to influence study outcomes, including, but not limited to, age, gender, vestibular function. For the intention-to-treat mixed-effects models, an unstructured error covariance structure will be utilized and parameters will be estimated using restricted maximum likelihood procedures. Missing data points in the analytical sample are considered missing at random and the above approach is sufficient under this assumption. Results will be considered significant at $\alpha=0.05$ with Holm-Bonferroni adjustments to correct for multiple comparisons among the various outcome measures. Model fit and integrity will be examined using a combination of formal fit criteria and visual inspection of residual plots.

Secondary Outcome measures will be assessed using the mixed-effects models as described above to determine the effect of time and treatment on each outcome. To determine the meaningful change of head stability metrics after rehabilitation, the minimal detectable change of our novel outcome measures presented in Table 2 such as attenuation coefficient, cross-covariance of eye, head, and lumbar movements, peak axial rotational velocities, and sequential timing of reorientation will be calculated. Minimally clinically important difference for these novel measures will also be calculated using an anchor-based approach where clinically meaningful difference is based on PGIC.

9. Privacy, Confidentiality, and Data Security

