Statistical Analysis Plan for DOD2: Can Early Initiation of Rehabilitation With Wearable Sensor Technology Improve Outcomes in mTBI?

NCT03479541

April 17, 2024

Statistical Analysis Plan

To evaluate differences in primary and secondary outcomes (all but Patient Global Impression of Change and Dynamic Visual Acuity), we used linear mixed-effect (LME) models with an intention-to-treat design. This statistical approach factors in the 6-week wait as well as the intervention time for the later physical therapy (PT) group, and allowed us to include data from all participants even those who withdrew or were lost to follow-up. Each LME model contained fixed effects for PT onset group (earlier or later PT), time since injury, and the group x time since injury interaction. The interaction effect examined the difference of change in the outcomes over time based on the group. The later PT group served as the reference. Both linear and quadratic time since injury were assessed in the model, and linear time was included in the final model. The full LME models also included apriori covariates of age, gender, and initial SCAT symptom severity total score, and random intercepts to account for within-participant correlations. Outcomes were assessed for normality assumptions in the LME models and were log transformed if necessary. We accounted for participants that withdrew or were lost to follow-up using inverse probability weighting in the model and sensitivity analyses were performed for inverse probability weights.

Primary Outcome

- 1) Dizziness Handicap Inventory (DHI)

Secondary Outcomes:

- 2) Neurobehavioral Symptom Inventory (NSI)
- 3) Quality of Life After Brain Injury (QOLIBRI)
- 4) Return to Activity Question
- 5) Vestibular/Ocular-Motor Screening (VOMS) Tool
- 6) Mini-Balance Evaluation Systems Test (Mini-BESTest)
- 7) Modified Balance Error Scoring System (mBESS)
- 8) Automated Neuropsychological Assessment Metrics (ANAM)
- 9) Instrumented Sway
- 10) Instrumented Walking
- 11) Complex Navigation Task
- 12) Central Sensorimotor Integration (CSMI) Test
- 13) Auditory Processing

Other Pre-specified Outcomes

- 14) Post-concussion Symptom Scale From the Sport Concussion Assessment (SCAT) Tool Version 5
- 15) Insomnia Severity Index (ISI)
- 16) Head Impact Test (HIT) – 6

Statistical Analysis Plan for Patient Global Impression of Change (Secondary Outcome)

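### The DHI group-by-time test rests on random intercepts with no stated standard error method; if model-based errors and the 6-month visit were used, its standard error may be wrong in either direction

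*SAP*

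**What the plan says.** The SAP's opening section fits the DHI, and every other outcome except the Patient Global Impression of Change and Dynamic Visual Acuity, with fixed effects for timing group, time since injury and their product. Quadratic time was examined and linear time kept. On the product term it says: "The interaction effect examined the difference of change in the outcomes over time based on the group". The last items in the model are "initial SCAT symptom severity total score, and random intercepts to account for within-participant correlations". On dropout it says: "We accounted for participants that withdrew or were lost to follow-up using inverse probability weighting in the model". The sensitivity analyses it mentions concern the weights. It states no residual covariance, no standard error method and no list of visits.

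Protocol section 8 (Study design for Aims I and II) says of the intention-to-treat models that "an unstructured error covariance structure will be utilized and parameters will be estimated using restricted maximum likelihood procedures".

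The protocol schedules a late visit in three places. Section 2, Aim I: "People will be tested before and after a 6-week rehabilitation program and again 6 months later to determine long-term effects". Section 6, Aim I & II: "the second follow up session will be an additional 6 months later". Section 6, Post testing: "The follow-up session will be an additional 6 months later and will encompass the same testing protocol as the posttest session". The mobility session, under which the questionnaires including the DHI are listed, opens with "The following tests and procedures will be performed a maximum of 4 times, depending on which physical therapy group participants were randomized into". That fits three test occasions in the early arm and four in the later arm.

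**The concern.** The primary comparison is a difference between two slopes, so its standard error depends on how each person's measurements co-vary over time. Random intercepts with independent residuals impose compound symmetry: one variance at every visit, one correlation for every pair of visits, and one common slope within an arm. Three ordinary departures break this: people recover at different rates, neighbouring visits resemble each other more than distant ones, or the spread of scores changes with recovery. An unstructured covariance, as the protocol planned, allows for all three.

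The trial itself gives a reason why slopes might vary. Aim II randomises people within each timing arm to home exercise with or without sensors and expects sensors to help, yet the SAP model has no sensor term.

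At stake are the width of the confidence interval and the error rate of the primary test. The Dynamic Visual Acuity model uses only the pre-therapy and post-therapy time points, so the question of the 6-month visit does not arise there.

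**Working it through.** The plan gives no type I error figure to reproduce. The check asks how far the model-based standard error departs from the true one.

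**From the documents.** Six weeks of therapy, a 6-week wait in the later arm (SAP), a visit 6 months after therapy, an extra pre-therapy visit in the later arm, and 160 recruited and split in half, so 80 per arm.

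**Assumed (not in the documents).** Six months = 182 days. Visits in days after the first test: early 0, 42, 224 (42 + 182); later 0, 42, 84, 266 (84 + 182). Between-person SD 15 and residual SD 10 DHI points. True mean linear and equal in both arms. Only the ratios of the SDs matter, so the results also hold on a log scale with the same ratios.

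**Method (large sample).** Let Σ be the true covariance of one person's visits and X = [1, t].
1. Find the V = τ²J + σ²I that the random-intercept fit converges to, by minimising the sum over arms of log|V| + tr(V⁻¹Σ).
2. In each arm A = (X′V⁻¹X)⁻¹. The model-based slope variance is proportional to A₂₂, and the true one to [A X′V⁻¹ΣV⁻¹X A]₂₂. The interaction is the difference of the two arm slopes, so the variances add over arms.
3. R = √(model-based ÷ true). Type I error = 2Φ(−1.96 R).

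Example, slope SD 10 with the 6-month visit: R = 0.875, 1.96 × 0.875 = 1.715, 2Φ(−1.715) ≈ 0.086.

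| True covariance beyond the random intercept | R, with 6-month visit | Type I error, with | Type I error, without |
|---|---|---|---|
| None (compound symmetry) | 1.000 | 5.0% | 5.0% |
| Slope SD 5 per 224 days | 0.957 | 6.1% | 5.0% |
| Slope SD 10 | 0.875 | 8.6% | 5.0% |
| Slope SD 15 | 0.805 | 11.5% | 5.0% |
| Equal slopes, residual correlation decaying exponentially, 30 days | 0.921 | 7.1% | 4.9% |
| Same, 60 days | 0.841 | 9.9% | 4.9% |
| Same, 120 days | 0.781 | 12.6% | 4.8% |
| Equal slopes, residual SD falling linearly from 10 to 5 by day 224 | 1.184 | 2.0% | 5.5% |

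The last row is a standard error 18% too large; the other departures make it too small.

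**Sensitivity to the SDs.** With between-person SD 10 to 20, residual SD 7 to 15 and the 6-month visit, slope SD 5, 10 and 15 give 5.5 to 7.1%, 6.8 to 11.1% and 8.7 to 14.3%.

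**Simulation check** (80 per arm, 4,000 trials per setting, 6-month visit, slope SD 0/5/10/15):
- Complete data: model-based 4.3/6.3/8.7/11.6%, participant-clustered 4.5/5.5/5.3/4.8%.
- 20% dropout, the SAP covariates and inverse probability weights: 4.9/6.6/9.3/12.2% against 5.0/5.4/5.2/5.1%.

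A second simulation used residual SD 8, slightly different visit weeks and slope SD 0.1 to 0.8 points per week. Model-based tests rejected 7.3 to 18.7% and clustered tests 5.2 to 6.1%. Without the 6-month visit, and with slope SD 0 to 0.8, the model-based test rejected 5.3 to 6.2%. At slope SD 0.3 the inflation was similar without weighting (10.8% against 11.4%), so it comes from the covariance and not from the weights.

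**Limit of clustering.** Suppose both arms share an assumed 20-point exponential recovery (56-day constant) with equal slopes. Because the arms are measured at different times and time enters linearly, clustered tests then reject about 42% with the 6-month visit and 35% without it.

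**The case against.** The strongest reply is that no error has been shown. The documents give no standard error method, no visit list and no DHI variances, so every percentage rests on assumed values. The SAP never mentions the 6-month visit; it speaks only of the wait and the intervention time. If only that period is modelled, the test is close to nominal. The SAP is also short and written in the past tense, and it omits REML and the significance level too. Silence on residual covariance may be thin reporting and not a change of method. All of this stands, and it limits the point to a safeguard and a request for disclosure.

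A reader might infer three stronger things that the documents do not support:
- That the primary test is shown to reject too often. The direction is unknown: shrinking residual spread gives 2.0%.
- That the interval is sound as long as everyone within an arm recovers at the same rate. Serially correlated residuals with equal slopes give 7.1 to 12.6%.
- That clustered standard errors make the test safe in general. They do so only if the mean is truly linear. The SAP says quadratic time was assessed, but neither document gives the result.

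On the other side, the SAP restricts visits to pre-therapy and post-therapy only for Dynamic Visual Acuity. That suggests, without proving, that the DHI model has no such restriction.

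**Conclusion.** The point holds as a conditional one. The SAP's stated covariance is narrower than the protocol's, the change is unexplained, and the standard error method is missing for the primary test. If model-based errors were used and the 6-month visit was included, the interaction's standard error is in general wrong unless the within-person covariance is compound symmetric. Under the assumed SDs, type I error then ranges from 2.0% to 12.6%, depending on which departure applies. At slope SD 5 the effect is only about 1 percentage point. Without the 6-month visit it stays at 4.8 to 5.5% in the same settings. The change should be made because it is cheap and removes a dependence that the reader cannot check, not because the reported result is known to be wrong. Confidence is medium, since the true DHI variances and the visits modelled are not given.

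**What to change.** - Report participant-clustered robust standard errors for the group by time test on the DHI, and on the other outcomes that share this model and include the 6-month visit.
- State which visits entered each model, the residual covariance and the standard error method, and why the protocol's covariance was left. If clustered errors were already used, saying so settles the point.
- Show the protocol's unstructured-covariance REML model alongside, labelled as the protocol-specified analysis and not as post hoc. A random-slope fit is an optional post hoc sensitivity analysis.
- Label as post hoc any change from the standard errors already used, since the SAP describes a completed analysis.
- Say that clustering corrects the variance only. Whether a linear trend is adequate, with arms measured at different times, needs its own check.

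The cost is two or three sentences and a re-fit of existing data. The interval widens when slopes vary or residuals are serially correlated. In simulation with the 6-month visit the clustered standard error was 0/4/14/24% larger at slope SD 0/5/10/15, and without that visit it agreed with the model-based one within 0.5%.

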Aim I & II: subjects will be compensated on a graduated scale to encourage retention. The first visit consisting of vestibular and oculomotor tests will be compensated \$40. The second session, consisting of the baseline mobility and further oculomotor tests, will be compensated \$60. The post-therapy mobility and oculomotor session will be compensated \$80, and the retention mobility and oculomotor session will be compensated \$100. Participants will be compensated \$10 dollars per visit for each rehabilitation session. There is a maximum of 5 testing sessions, and approximately eight rehabilitation sessions. Subjects randomized into the standard of care intervention will be tested for mobility and oculomotor at both baseline and prior to starting their physical therapy. Therefore, the standard of care group will have an additional session for which they will be compensated \$60. If a subject does not complete all parts of a session they will be compensated a prorated amount for their time based on the compensation for that session. People who complete all sessions for Aim I & II will be compensated \$275 if they are randomized into the early intervention group, or \$335 if they are randomized into the standard of care group.

Adaptation during COVID- 19 restrictions: Participants will be compensated \$10 for rehab, \$20 for modified Day 1, and \$30 for modified follow up testings. People that complete all modified sessions will be compensated up to \$190.

Home monitoring: Participants will be compensated \$10/per day for approx. 7 days= \$70. This will take place at two different time points during the study for a maximum compensation of \$140.

Aim III: Physical Therapists will be compensated \$100 for their time in training as well as testing. Both people with mTBI and healthy controls will be compensated \$25 for the 60-minute long session

f. Consent Process

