Headache Impact Test- 6 (HIT-6): This questionnaire measures one's ability to function in everyday life (work, school, home and social situations). This questionnaire takes five minutes.

Quality of Life After Brain Injury (QOLIBRI): This questionnaire takes approximately 10 minutes and will ask them to rate your quality of life before and after concussion.

Concussion Symptom Subtype Inventory (CSSI): This questionnaire takes approximately 10 minutes and asks you to rate if you have had specific symptoms within eight categories at two points in time – before your injury and now.

Patients Global Impression of Change (PGIC): This single questionnaire takes approximately 1 minute and will ask people to rate how they perceive their health has changed over the course of treatment on a scale of 1-7.

Home monitoring: A subset of participants will be given an inertial sensor to wear at home for a period of time (i.e. 7 days) to follow their activity recovery at home.

Adaptation during COVID- 19 restrictions: Modified procedures during this time will be for study team members to ask questionnaires (listed above) over the phone or through a virtual visit. Participants will be emailed a PDF of the questionnaires for them to review while the study team member asks them to subjectively rate their symptoms.

Intervention: After participants are enrolled in the study, they will be randomly assigned to begin physical therapy immediately (approximately 2 weeks after their physician appointment) or within the standard of care timeline (approximately 8 weeks after their physician appointment). This randomization will be found on a pre-assigned list that was generated prior to their enrollment. This randomization will be performed in RedCap by a

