The Patient Global Impression of Change (PGIC) is an ordinal variable where participants rate their global assessment of change on a scale from 1 to 7. To test whether the group with Earlier PT had larger improvements in the PGIC than the Later PT group, we conducted a Mann-Whitney U test to assess group differences in PGIC scores.

Statistical Analysis Plan for Dynamic Visual Acuity (Secondary Outcome)

We used a linear mixed-effect (LME) model with an intention-to-treat design. The LME model contained fixed effects for PT onset group (earlier or later PT), time point (pre-PT or post-PT), and the group x time point interaction. The interaction effect examined the group difference of change in the outcomes between time points. The later PT group and pre-PT time point served as the references. The full LME model also included apriori covariates of age, gender, initial SCAT symptom severity total score, days since injury before starting PT, and random intercepts to account for within-participant correlations. Outcomes were assessed for normality assumptions in the LME models and were log transformed if necessary. We accounted for participants that withdrew or were lost to follow-up using inverse probability weighting in the model and sensitivity analyses were performed for inverse probability weights.

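### The dynamic visual acuity interaction compares change over about weeks 2–8 (earlier PT) with change over about weeks 8–14 (later PT), so natural recovery can look like an effect of timing

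*SAP*

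**What the plan says.** The SAP gives DVA a section and a model of its own. The fixed effects are "fixed effects for PT onset group (earlier or later PT), time point (pre-PT or post-PT), and the group x time point interaction". The purpose is stated openly: "The interaction effect examined the group difference of change in the outcomes between time points". Adjustment is for "apriori covariates of age, gender, initial SCAT symptom severity total score, days since injury before starting PT, and random intercepts".

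The other outcomes, apart from the Patient Global Impression of Change, use a model on the time-since-injury scale. The SAP says of it: "This statistical approach factors in the 6-week wait as well as the intervention time for the later physical therapy (PT) group". DVA is excluded from that model and no reason is given.

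Protocol section 6 (Intervention) starts therapy "approximately 2 weeks after their physician appointment) or within the standard of care timeline (approximately 8 weeks after their physician appointment". It lasts 6 weeks, and the first follow-up test comes directly afterwards.

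The later arm has an extra test session. Protocol section 5e (compensation) says this group "will be tested for mobility and oculomotor at both baseline and prior to starting their physical therapy". Section 6 (Aim I & II) instead describes "one additional balance and gait testing session just prior to beginning rehabilitation". The mobility and coordination session in section 6 includes an eye-chart test with head movement and is run up to four times, but DVA is not named there. The SAP does not say which later-arm test counts as pre-PT.

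**The concern.** Aim I asks whether starting rehabilitation earlier gives better outcomes. Participants enter less than 12 weeks after concussion, so many may still be recovering without therapy. A contrast anchored on each person's own therapy start places the two arms in different stretches of that recovery. The later arm's reference value is also taken after randomisation and after about 6 weeks of waiting, so it is not a baseline in the usual sense.

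If recovery is quicker at first and then slows, the earlier arm shows more pre-to-post change even when the start date makes no difference. A significant interaction could then be reported as evidence for earlier PT when it reflects only the calendar.

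**Working it through.** **Windows.** The gap between starts is 8 − 2 = 6 weeks, which reproduces the SAP's 6-week wait. Adding 6 weeks of therapy gives weeks 2–8 (earlier) and 8–14 (later), counted from the physician visit. With the Protocol's alternative of about 60 days, the later window is 8.6–14.6. The windows meet only at week 8.

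**The covariate.** Days from injury to the start of PT takes one value per person and enters only as a main effect. In a complete pre/post pair it cancels from the within-person change, and the interaction is estimated from those changes. Random-intercept fits to simulated complete data confirm this: the interaction was −0.1468 (SE 0.1646) with and without the covariate. In a separate set of 150 simulated trials the largest difference between the two fits was 6e-15.

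**Size under no timing effect.** The following are assumptions, not figures from the documents, except that n uses the Protocol's totals:
- natural change in the early window: 0.5 SD
- SD of the change score: 1
- n = 64 per arm: half of 160 is 80, less about 20% dropout (80 × 0.8)
- recovery: exponential with time constant τ, or linear

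The later window begins 42 days after the earlier one, so natural change there is q = exp(−42/τ) times that in the early window (q = 1 if linear). The spurious difference is 0.5 × (1 − q). Rejection rates come from a two-sided two-sample t-test on change scores (noncentral t).

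| Recovery | q | Spurious difference, SD (toward earlier PT) | Null rejected, alpha 0.05 |
|---|---|---|---|
| τ = 30 days | 0.247 | 0.38 | 56% |
| τ = 60 days | 0.497 | 0.25 | 29% |
| τ = 120 days | 0.705 | 0.15 | 13% |
| linear | 1 | 0 | 5% |

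**Sensitivity**, in the same order of curves:
- 40 per arm (an assumption; COVID-period testing was by questionnaire): 38%, 20%, 10%, 5%.
- 0.25 SD natural change, 64 per arm: 19%, 11%, 7%, 5%.
- Strictest Holm step over 15 outcomes (DHI, 12 listed secondary outcomes, global impression of change, DVA): 20%, 6%, 2%, 0.3%.
- A different calibration fixes a 1 SD deficit at the physician visit, with half-life h in weeks. The difference is then [2^(−2/h) − 2^(−8/h)] − [2^(−8/h) − 2^(−14/h)]. At h = 8 this is 0.341 − 0.203 = 0.14 SD. For h = 2, 4, 8, 12 and 26 it is 0.38, 0.30, 0.14, 0.08 and 0.02 SD.

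**Which later-arm test is pre-PT.** If the enrolment test were used instead, the later window would be about weeks 2–14 and the spurious difference −0.5q, that is −0.12, −0.25, −0.35 or −0.50 SD, now toward later PT. The undefined term therefore affects the sign.

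**Would the main model's linear slope cure it?** The SAP says of that model: "Both linear and quadratic time since injury were assessed in the model, and linear time was included in the final model". Taking the physician visit at day 10 (the Protocol's clinic-sample average), the earlier arm is tested at days 24 and 66. The null slope difference per 42 days depends on the visits available:
- Later arm at days 66 and 108 only: 0.38, 0.25, 0.15, 0 SD (all of the bias).
- Later arm at days 24, 66 and 108: 0.19, 0.13, 0.07, 0 SD (half of it).
- With 6-month tests added (earlier day 249, later day 291): 0.02, 0.03, 0.03, 0 SD.

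**The case against.** The best defence is that the SAP misstates nothing. It defines the interaction as a difference in change between two time points and claims no equality of elapsed time. Change across therapy, compared between arms formed by randomisation, is a legitimate if limited estimand. This stands, and it is why the point concerns what the result can be used to show.

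The defence can add that the size is not identified. Fixing 0.5 SD natural change for every curve implies different starting deficits (0.66, 0.99 and 1.69 SD at day 24 for τ = 30, 60 and 120). That is fair. The figures show what could happen, and the bias is zero under linear recovery.

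It can also say that later-arm enrolment DVA may not exist, and that a two-level factor is what one would use if DVA was measured only before and after therapy. The Protocol does not settle this. In that case only the definition and the labelling can be fixed. Nor does a week-8 comparison answer Aim I's question, since it tests therapy against not yet having had therapy.

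A reader might go further and infer that the DVA result must be biased toward earlier PT, or that randomisation is broken. Neither follows. The direction depends on an unknown recovery curve and an undefined term, and the arms remain randomised; what is lost is comparison over the same elapsed time. A reader might also carry the finding over to the Dizziness Handicap Inventory (DHI), or conclude that the DHI is safe. The DHI model does not use this pre/post contrast, but its linear slope is not automatically free of bias under curved recovery. Nothing here measures that.

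**Conclusion.** The concern holds in limited form. On the natural reading that pre-PT is the test just before therapy, the SAP's only DVA comparison by onset group uses windows about 6 weeks apart and mixes therapy effect with natural recovery. It can therefore differ from zero when timing has no effect, and the days-to-PT covariate leaves it unchanged in complete pairs.

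Under the main assumptions the spurious difference runs from 0 to 0.38 SD and the rejection rate from 5% to 56%. The real size is unknown. DVA is one secondary outcome among many, so this deserves correction but does not threaten the primary analysis by this route. Confidence is medium, because the meaning of pre-PT and the actual DVA visit schedule are not stated.

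**What to change.** 1. State in the SAP which later-arm test is the pre-PT value.
2. Report the existing interaction as the group difference in change during PT, not as evidence on earlier versus later timing.
3. Check whether later-arm enrolment DVA was collected. Protocol section 5e and the four-fold mobility session in section 6 suggest it may have been; the balance-and-gait description of the extra session does not. If it exists, add the randomised comparison over the same elapsed time: enrolment value as baseline in both arms, outcome at about week 8 (earlier arm post-PT, later arm just before PT), labelled PT versus not yet PT. Under a common recovery curve the natural-recovery difference in this contrast is zero.
4. If 6-month DVA also exists, DVA can be analysed on the time-since-injury scale, with time allowed to curve. A shared quadratic is not exact either: with the 6-month visits, its null group-by-time term is −0.04, −0.03 and −0.02 SD per 42 days for the three exponential curves. With only pre and post visits, do not simply adopt the linear slope.

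The cost is one or two SAP sentences and, if the enrolment data exist, a small re-analysis. The downside is a narrower claim for DVA.
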